5.4.4 Record of administration

Accurate records will be kept in the source documents of all drug administration (including dispensing and dosing). Time and rate changes of Ofatumumab infusions will be recorded only during management of infusion related reaction.

5.5 Dose Continuation, Modification and Interruption

Subjects will be evaluated for AEs at each visit with the NCI CTCAE v4.03 (see Appendix 4: NCI CTCAE v4.03) used as a guide for the grading of severity. Sections below describe dose reduction steps, instructions for initiation of a new cycle of therapy and dose modifications during a cycle of therapy.

5.5.1 Dose Modification Steps for GSK2110183

GSK2110183 dose reductions should be taken one dose level at a time per the table below.

Dose levels for GSK2110183:

Dose level	Daily dose (mg)
Dose level 0 (starting dose)	125
Dose level -1	100
Dose level -2	75
Dose level -3	50
Dose level -4	25

5.5.2 Instructions for initiation of a New Cycle

A new course of treatment may begin on the scheduled Day 1 of a new cycle if:

- The ANC is $\geq 0.5 \times 10^9/L$;
- The platelet count is $\geq 30 \times 10^9/L$;
- Any drug-related rash, diarrhea, dyspepsia, mucositis or infection that may have occurred has resolved to \leq **grade 1** severity (see Section 5.5.3.2);
- Any drug-related toxicity that may have occurred has resolved to \leq **grade 2** severity

If these conditions are not met on Day 1 of a new cycle, the subject will be evaluated weekly and a new cycle of treatment will not be initiated until the toxicity has resolved as described above. If the toxicity does not resolve to \leq Grade 2 or baseline within 14 days, withdrawal from the trial is recommended. However, if the investigator agrees that further treatment will benefit the subject,

treatment can continue with at least one-level dose reduction once the toxicity resolves to \leq Grade 1 or baseline.

If GSK2110183 dose reduction was taken during the previous cycle and the cycle was completed without requiring further dose modification, then the next cycle will start at the same reduced dose of GSK2110183. If ofatumumab or GSK2110183 dosing was omitted for the remainder of the previous cycle or if the new cycle is delayed due to toxicity newly encountered on the scheduled Day 1, then the new cycle will be started with a one-level dose reduction of GSK2110183, based upon which drug was felt by the investigator to be most responsible for the toxicity.

EXCEPTIONS:

For toxicities specific to either ofatumumab or GSK2110183, see Section 5.5.3

For hematopoietic toxicities (neutropenia, thrombocytopenia), only GSK2110183 will undergo dose reductions. Ofatumumab will not be dose-reduced for cytopenias.(see Section 5.5.3.1).

If GSK2110183 dosing is delayed for $ANC < 0.5 \times 10^9/L$ on Day 1 of a new cycle, the option of initiating GCSF support may be taken (see Section 5.5.4).

5.5.3 Instructions for dose modifications or interruption

5.5.3.1 Ofatumumab

Dose delay and dose reduction rules for ofatumumab are as follows and in the table below.

- There will be no ofatumumab dose reductions. Infusional reactions will mandate infusion rate modifications (Section 5.4.3).
- For treatment interruptions during a cycle, the 28-day schedule of each cycle will continue to be followed. Missed doses of ofatumumab are not made up.
- For treatment interruptions that delay the scheduled start of a new cycle, when toxicity has resolved as required to allow the start of a new cycle (Section 5.5.2), the restart day of therapy becomes Day 1 of the next cycle.
- There will be no dose reductions of ofatumumab for hematopoietic toxicity (neutropenia, thrombocytopenia). Only GSK2110183 will be dose-reduced for cytopenic toxicity (see Section 5.5.4)
- If GSK2110183 is held for toxicities at the *start of a new cycle*, ofatumumab will also be held until toxicities resolve and allow the new cycle to initiate with both agents.

- If GSK2110183 is held for toxicities in the *middle of a cycle*, ofatumumab may continue **without interruption**, providing the investigator feels that ofatumumab is not contributing to the toxicities.

NOTE: Discontinuation of ofatumumab for infusional adverse events will warrant patient removal from study. If the lowest dose level of GSK2110183 is not tolerated for GSK2110183-related toxicity, the patient may continue on study with ofatumumab alone.

5.5.3.2 GSK2110183

Dose delay and dose reduction rules for GSK2110183 are as follows and in the table below.

- GSK2110183 dose reduction steps are outlined in Section 5.5.1.
- For treatment interruptions during a cycle, the 28-day schedule of each cycle will continue to be followed. Missed doses of GSK2110183 are not made up.
- For treatment interruptions that delay the scheduled start of a new cycle, when toxicity has resolved as required to allow the start of a new cycle (Section 5.5.2), the restart day of therapy becomes Day 1 of the next cycle.
- If ofatumumab is held at the start of a new cycle, GSK2110183 should also be held.

5.5.4 Dose modifications for GSK2110183 (specific toxicities):

Table 1. Specific hematologic toxicities:

Neutropenia	Intervention
Grade 1 – 2	None
Grade 3 neutropenia with fever (temperature $\geq 38.5^{\circ}$ C) or Grade 4 neutropenia	
Hold (interrupt) both study drugs and follow CBC weekly. When neutropenia has resolved to \leq grade 2, then resume GSK2110183 dose at next lower dose level (no dose reduction for ofatumumab).
 
Instead of waiting for neutrophil recovery, there is an option to use GCSF 300ug SC OD until neutropenia has resolved to \leq grade 2, then resume GSK2110183 dose at next lower dose level (no dose reduction for ofatumumab).
 
If more than one event of Grade 3-4 neutropenia occurs (i.e. more than one dose reduction of GSK2110183 is undertaken), there is an option to use GCSF 300ug SC once or twice weekly continuously as secondary prophylaxis.

Thrombocytopenia	Intervention
Grade 1 – 3	None
Grade 4 (<25,000/uL)	
Hold (interrupt) both study drugs and follow CBC weekly.
 
When thrombocytopenia has resolved to \leq grade 2, then resume GSK2110183 dose at next lower dose level (no dose reduction for ofatumumab).

Table 2. Specific non-hematologic toxicities:

Hyperglycemia	Intervention
Grade 1 – ULN-8.9 mmol/L	None
Grade 2 - >8.9-13.9 mmol/L	
Monitor blood glucose weekly (either with portable glucometer or with chemistry testing).
 
If Grade 2 hyperglycemia recurs, then decrease GSK2110183 by one dose level immediately and carry over into the subsequent cycle.
 
If Grade 2 hyperglycemia recurs within new cycle, decrease GSK2110183 by one dose level immediately and carry over into the subsequent cycle. Continue dose reductions (max once per cycle) until no episodes of Grade 2 hyperglycemia are documented within the new cycle.
 
If dose level -4 is reached and Grade 2 or higher hyperglycemia recurs, discontinue GSK2110183.

Grade 3 - >13.9-27.8 mmol/L	
Check for ketoacidosis: If present, discontinue therapy and treat as for diabetic ketoacidosis.
 
If no acidosis, hold drug and treat with oral hypoglycemics or insulin as needed. Monitor blood glucose daily (or more as per physician discretion).
 
If no further grade 3 hyperglycemia recurs over 7 successive days of monitoring, GSK2110183 may be restarted at one dose level reduction.
 
Repeat above instructions for recurrent Grade 3 hyperglycemia.
 
If dose level -4 is reached and Grade 3 or higher hyperglycemia recurs, discontinue GSK2110183.

Grade 4 - >27.8 or acidosis	Discontinue GSK2110183

Table 3. Other specific toxicities:

Other specific toxicities	Intervention
Infection grade \geq 1 or 2	Hold (interrupt dose). Follow weekly Categorize infection: If grade 1 or 2, resume when controlled at previous dose at the investigator's discretion.
Infection \geq grade 3	If infection is grade 3, when it resolves to grade \leq 1, restart therapy with 1 dose level reduction.
Diarrhea \leq grade 2 (presumed secondary to drug – must rule out infectious causes)	Initiate loperamide 2mg po q2h while awake (max 16mg per 24 hour period). If diarrhea-free for >12 hours, discontinue loperamide. If diarrhea \leq grade 2 recurs within the same cycle, hold (interrupt dose) and use loperamide as above. When diarrhea resolves to \leq grade 1, drug may be resumed at a one dose level reduction.
Diarrhea \geq grade 3 or associated with dehydration (presumed secondary to drug – must rule out infectious causes)	Hold (interrupt dose) for remainder of cycle and hydrate. If diarrhea resolves to \leq grade 1, drug may be resumed with next cycle but at a one dose level reduction. If > grade 3 diarrhea recurs , repeat above and reduce by one dose level again. If again >grade 3 diarrhea recurs , patient will be removed from study .

Dyspepsia \leq grade 2	Initiate proton pump inhibitor or H2 blocker but proceed with current study drug dose. No dose reductions are required as long as symptoms resolve to \leq grade 1. If dyspepsia \leq grade 2 persists, decrease drug by one dose level. Continue with dose reductions if dyspepsia \leq grade 2 persists. When symptoms resolve to \leq grade 1, drug may be continued at the current dose level reduction.
Dyspepsia \geq grade 3	Hold (interrupt dose) until symptoms are controlled. Add proton pump inhibitor or H2 blocker. When symptoms resolve to \leq grade 1, drug may be resumed at a one dose level reduction.
Mucositis \leq grade 2	Initiate bicarbonate mouthwashes and mycostatin mouthwash. If mucositis \leq grade 2 persists, decrease drug by one dose level. Continue with dose reductions if mucositis \leq grade 2 persists. When symptoms resolve to \leq grade 1, drug may be continued at the current dose level reduction.
Mucositis \geq grade 3	Hold (interrupt dose) until symptoms are controlled. Initiate bicarbonate mouthwashes and mycostatin mouthwash. When symptoms resolve to \leq grade 1, drug may be resumed at a one dose level reduction.
Rash \leq grade 2	Hold (interrupt dose) until rash has resolved to \leq grade 1, then resume previous dose. If \leq grade 2 rash recurs, hold (interrupt dose) until rash has resolved to \leq grade 1, then resume dose at a one dose level reduction.
Rash grade 3	Hold (interrupt dose) for remainder of cycle. If rash has resolved to \leq grade 1, drug may be resumed at one dose level reduction. If grade 3 or higher rash recurs, patient will be removed from study.
Rash grade 4	Discontinue drug and patient will be removed from study.
Other non-hematologic toxicity assessed as study drug-related \geq Grade 3	Hold dose and follow at least weekly. When toxicity resolves to \leq grade 2 , restart at next lower dose level.

Progressive Multifocal Leukoencephalopathy (PML)

Progressive multifocal leukoencephalopathy (PML) is a viral-induced demyelinating disease of the central nervous system usually occurring in the immunocompromised individual. JC virus infection resulting in PML and death has been reported in rituximab-treated subjects with hematologic malignancies or with systemic lupus erythematosus (SLE), an indication for which rituximab has not been approved. In the literature, PML has been reported to occur in 0.52% of CLL subjects and in approximately 5% of fludarabine-treated B-CLL subjects. One case of PML was reported in a very ill CLL subject treated with ofatumumab, previously treated with alemtuzumab and fludarabine and with very low CD4 cell count.

Investigators and nurses should pay careful attention for signs and symptoms consistent with a diagnosis of PML. Signs and symptoms of PML include visual disturbances, ocular movements, ataxia, and changes in mental status such as disorientation or confusion. These symptoms are not an exhaustive list and the investigator should exercise judgment in deciding to report signs and symptoms to sponsor promptly.

If a subject develops neurological signs or symptoms consistent with PML treatment should be halted and the subject referred to a neurologist for evaluation. At a minimum, blood JCV PCR and/or MRI will be performed and if either is positive perform Cerebrospinal Fluid (CSF) JCV PCR. If blood JCV PCR and MRI are negative, the investigator will contact the GSK for appropriate action to be taken. If blood JCV PCR and/or MRI are positive, the subject should proceed to the Follow-Up Period. All such subjects will be followed until resolution. Any subject with a diagnosis of PML will be withdrawn from ofatumumab. There are no known tests that can reliably determine who is at increased risk for developing PML. There are no known interventions that can reliably prevent PML or adequately treat PML if it occurs.

Hepatitis B Virus (HBV) reactivation

Hepatitis B Virus (HBV) reactivation can occur in patients receiving CD20-directed cytolytic antibodies, including ARZERRA (Ofatumumab), in some cases resulting in fulminant hepatitis, hepatic failure and death.

In patients who develop HBV reactivation while receiving ofatumumab, immediately discontinue ofatumumab and start appropriate treatment for HBV, discontinue any concomitant chemotherapy the patient is receiving until the HBV infection is controlled or resolved. Due to insufficient data, no recommendations can be made regarding the resumption of ofatumumab after resolution of HBV in patients who develop HBV reactivation.

The risk of HBV infection and hepatitis can occur in patients who have not been previously exposed to HBV.

5.5.5 Treatment compliance

At all times, when dispensing protocol therapy, the study coordinator will review the instructions with subjects. Subjects will be asked to maintain a diary to record the drug administration. Subjects will be asked to bring any unused drug and empty drug containers to the clinic at their next visit.

Research personnel will count and record the number of used and unused drug at each visit and reconcile with the patient diary.

5.6 Concomitant therapy

5.6.1 Recommended concomitant therapy

Subjects should receive full supportive care, including transfusions of blood and blood products, antibiotics, hematopoietic growth factors, and antiemetics when appropriate. All patients will take allopurinol 300mg PO daily beginning at least 3 days before the start of GSK2110183 Lead-in Phase and continuing through 14 days of Cycle 1 on the Treatment Phase (minimum 27 days) for tumor lysis syndrome (TLS) prophylaxis. Subjects should be instructed to maintain adequate hydration and maintain urinary output as an additional measure to prevent TLS. Based on a patient's reaction and laboratory parameters, TLS prophylaxis may be continued or restarted as needed at the Investigator's discretion.

5.6.2 Prohibited concomitant therapy

Concomitant use of other anti-cancer therapies, including radiation, or other investigational agents is not permitted while subjects are receiving protocol therapy. In addition, GSK2110183 inhibits multiple cytochrome P450 (CYP) enzymes in vitro with CYP3A4 and CYP2C8 showing the lowest IC₅₀'s. GSK2110183 shows metabolism dependent inhibition of CYP3A4 and induced CYP3A4 in cultured human hepatocytes and GSK2110183 inhibits the human uptake transporter OATP1B1, as well as the human efflux transporter BCRP. As a result, other medications that may interact with GSK2110183 are prohibited or should be used with caution are outlined in Appendix 2.

5.6.3. Meals and Dietary Restrictions

On all blood sampling days, subjects will fast for at least eight hours prior to the blood draw for fasting glucose testing and other blood tests as required by Schedule of study events. Fasting will consist of avoiding the oral ingestion of calorie – containing products; however, ingestion of water and other non-caloric beverages is permitted.

Patients should fast 1 hr. before and 2 hrs. after each GSK2110183 dose. In addition, subjects shall abstain from ingestion of any food or drink containing grapefruit and grapefruit juice, Seville

oranges, or pommelos within 7 days prior to the first dose of GSK2110183 until the end of the study.

5.7 Discontinuation of Study Treatment

Treatment will continue until to a maximum of 18 cycles (months) or the occurrence of any of the following events.

- Disease progression (see Appendix 5 for IWCLL Response Criteria). If a study patient meets progressive disease criteria, study meds may be continued at investigator's discretion and after approval from the Study Medical Monitor, if it benefits the study patient.
- Adverse event(s) that, in the judgment of the Investigator, may cause severe or permanent harm or which rule out continuation of the treatment regimen (see Section 6.1)
- Major violation of the study protocol.
- Withdrawal of consent
- Lost to follow up
- Death

5.7.1 Stopping Safety Criteria

5.7.1.1 Liver Chemistry Stopping Criteria

Liver chemistry threshold stopping criteria have been designed to assure subject safety and to evaluate liver event etiology during administration of investigational product and the follow-up period. The sponsor-investigator is to review all events which meet liver chemistry stopping criteria to determine if the event was due to;

- tumor lysis, disease related liver involvement
- concomitant chemotherapy
- other identified cause and to exclude drug induced liver injury (DILI) due to Ofatumumab

The criteria are relevant for all Ofatumumab studies because transient elevations in LFTs may be due to tumor lysis which is of clinical benefit, disease related liver involvement or due to other chemotherapy rather than drug induced liver injury from Ofatumumab. If the event is determined to be due to causes other than Ofatumumab DILI and improvement is observed after withdrawal of

Ofatumumab, rechallenge may be attempted if deemed appropriate by the sponsor-investigator and in addition to consent of the subject.

Investigational product will be stopped if any of the following liver chemistry stopping criteria is met:

1. ALT $\geq 8 \times \text{ULN}$
2. ALT $\geq 5 \times \text{ULN}$ for more than 2 weeks
3. ALT $\geq 3 \times \text{ULN}$ and bilirubin $\geq 2 \times \text{ULN}$ (>35% direct bilirubin, bilirubin fractionation required[‡])

[‡] **NOTE:** *If serum bilirubin fractionation not immediately available, study drug should be discontinued if ALT > 3xULN and bilirubin > 2xULN. Serum bilirubin fractionation should be performed if testing is available. If testing unavailable, record presence of detectable urinary bilirubin on dipstick, indicating direct bilirubin elevations and suggesting liver injury.*

When any of the liver chemistry stopping criteria is met, do the following:

- Immediately stop study treatment
- Hold Ofatumumab for two weeks, repeat liver chemistry testing at least twice weekly, and report to sponsor-investigator to discuss the possibility of re-challenging with Ofatumumab. *Note: The 2 week time point for stopping medication was chosen because it will distinguish from LFT elevations due to tumor lysis which should have resolved within this time period. Medication is interrupted and it is a clinical and patient decision if Ofatumumab may be re-started. The risk: benefit ratio is different in an oncology setting and an efficacious therapy may be life-saving.*
- Report SAE to GSK within 24 hours
 - All events of ALT > 3xULN **and** bilirubin > 2xULN (>35% direct bilirubin) (or ALT > 3xULN and INR > 1.5, if INR measured; INR measurement is not required and the threshold value stated will not apply to subjects receiving anticoagulants), termed 'Hy's Law', **must be reported as an SAE (excluding studies of hepatic impairment or cirrhosis).**
 - NOTE: if serum bilirubin fractionation is not immediately available, study treatment should be discontinued if ALT > 3xULN **and** bilirubin > 2xULN. Serum bilirubin

fractionation should be performed if testing is available. If testing is unavailable, **record presence of detectable urinary bilirubin on dipstick**, indicating direct bilirubin elevations and suggesting liver injury.

Liver chemistry follow-up assessments are to be followed until liver chemistries resolve, stabilize or return to baseline values.

Liver Chemistry Follow-up Assessments; (these chemistry tests/ assessments below are to be performed at the time of the event and then continued and/or discontinued at the discretion/judgment of the sponsor-investigator; please refer to stopping criteria within this document below)

Viral hepatitis serology including:

- *Hepatitis A IgM antibody;*
- *Hepatitis B surface antigen and Hepatitis B Core Antibody (IgM);*
- *Hepatitis C RNA;*
- *Cytomegalovirus IgM antibody;*
- *Epstein-Barr viral capsid antigen IgM antibody (or if unavailable, obtain heterophile antibody or monospot testing);*
- *Hepatitis E IgM antibody*
- Serum creatine phosphokinase (CPK) and lactate dehydrogenase (LDH)
- Fractionate bilirubin, if total bilirubin >2xULN
- Obtain complete blood count with differential to assess eosinophilia
- Record the appearance or worsening clinical symptoms of hepatitis, or hypersensitivity, fatigue, decreased appetite, nausea, vomiting, abdominal pain, jaundice, fever, or rash
- Record use of concomitant medications, acetaminophen, herbal remedies, other over the counter medications, or putative hepatotoxins
- Increased alcohol use

The following assessments are required for subjects with ALT >3xULN and bilirubin >2xULN (.35% direct) but are optional for other abnormal liver chemistries:

- Anti-nuclear antibody, anti-smooth muscle antibody, and Type 1 anti-liver kidney microsomal antibodies
- Liver imaging (ultrasound, magnetic resonance, or computerized tomography) to evaluate liver disease.

Stopping Criteria:

- For subject meeting liver stopping criteria 1:
 - A repeat of liver chemistries within 24 hours, liver event follow-up assessments and close monitoring
 - A specialist or hepatology consultation is recommended
 - Monitor subjects twice weekly until liver chemistries (ALT, AST, alkaline phosphatase, bilirubin) resolve, stabilize or return to within baseline values.
- For subjects meeting criteria 2 or 3:
 - A repeat of liver chemistries within 24 to 72 hours for repeat liver chemistries and liver event follow-up assessments
 - Monitor subjects weekly until liver chemistries (ALT, AST, alkaline phosphatase, bilirubin) resolve, stabilize or return to within baseline values
- After holding Ofatumumab for two weeks:
 - If the treatment is exhibiting efficacy **and** the subject wants to continue therapy after being informed of the results of liver chemistry testing, then the Ofatumumab may be re-started.
 - Liver chemistries and follow-up assessments should be monitored at a minimum of every 2 weeks until resolution, stabilization, or a return to baseline values, at which point monitoring should be continued per protocol
- Subjects with ALT >3xULN **but** <5xULN **and** bilirubin <2xULN without hepatitis symptoms or rash, and who may be monitored weekly for at least 4 weeks, then the following actions should be taken:
 - Subjects can continue Ofatumumab

- Weekly repeat of liver chemistries until they resolve, stabilize, or return to baseline values, then monitor liver chemistries as per protocol assessment schedule

If at any time the subject meets any of the liver chemistry stopping criteria, then proceed as described above

If after 4 weeks of monitoring, ALT<3xULN and bilirubin<2xULN monitor twice monthly until liver chemistries normalize or return to within baseline values

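### After a liver stopping event, section 5.7.1.1 sets causality and restart conditions for ofatumumab only, leaving GSK2110183, the drug with the reported dose-limiting liver toxicity, without a liver-specific restart condition

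*Combined protocol and SAP*

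**What the plan says.** Section 5.7.1.1 lists three liver chemistry criteria. When one is met the instruction is "Immediately stop study treatment". On cause, "The sponsor-investigator is to review all events which meet liver chemistry stopping criteria to determine if the event was due to" tumor lysis or liver involvement by disease, "concomitant chemotherapy", or "other identified cause and to exclude drug induced liver injury (DILI) due to Ofatumumab". The section describes its own scope in these words: "The criteria are relevant for all Ofatumumab studies".

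The steps that follow are written for ofatumumab. The first action after the stop is "Hold Ofatumumab for two weeks, repeat liver chemistry testing at least twice weekly". If the cause is something other than ofatumumab injury and the patient improves once ofatumumab is withdrawn, "rechallenge may be attempted if deemed appropriate by the sponsor-investigator and in addition to consent of the subject". After the hold, if treatment is working and the informed patient wishes to go on, "then the Ofatumumab may be re-started".

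Other sections bear on GSK2110183:

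- Section 3.1 gives reversible changes in liver enzymes as its phase 1 dose-limiting toxicity.
- Section 5.1.2 says drug-related Grade 3 events were very few, and that AST and ALT abnormalities were the most frequent Grade 3 events.
- The dose-modification tables in 5.5.4 have no liver row. Their last row covers any other drug-related non-hematologic toxicity of Grade 3 or higher: hold, then resume one level lower once it is Grade 2 or below.

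**The concern.** The rule stops treatment as a whole but says how to resume only one of the two drugs, and the one it omits has the reported dose-limiting liver toxicity. The wording looks like a general ofatumumab rule that was not adapted to this combination. It lists chemotherapy as a possible cause, although 5.6.2 does not permit other anti-cancer therapy during protocol treatment. The second study drug can enter only as an unnamed other cause.

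What is at stake is patient safety and consistent handling. An investigator who follows the text could resume GSK2110183 after a liver injury that it caused, without breaching any condition in 5.7.1.1.

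**Working it through.** The plan states no figure to reproduce. The check sets the steps of 5.7.1.1 against the rules for GSK2110183 elsewhere.

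**1. Which drug each step names**

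| Step in 5.7.1.1 | Drug named |
|---|---|
| Stop | None (investigational product; study treatment) |
| Injury to exclude | Ofatumumab |
| Two-week hold | Ofatumumab |
| Rechallenge | Ofatumumab is the only drug named; the drug to be rechallenged is not stated |
| Restart after the hold | Ofatumumab |

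Four steps decide resumption. Four name ofatumumab and none names GSK2110183. Over the whole of 5.7.1.1, ofatumumab is named 11 times and GSK2110183 not once. The counts show the scope of the text, not the size of any harm.

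**2. The rechallenge sentence, taken literally.** Suppose GSK2110183 caused the event.

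- The cause is then not ofatumumab, so the causality condition is met.
- If both drugs were stopped together, improvement follows the withdrawal of ofatumumab whichever drug was responsible, so the second condition can be met too.
- Sponsor-investigator agreement and patient consent remain.

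The natural reading is that ofatumumab is rechallenged, and then the sentence says nothing about GSK2110183. A wider reading lets it cover GSK2110183, and then injury from that drug helps to justify giving it again.

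**3. The catch-all row in 5.5.4.** It applies only if the event is judged drug-related and is Grade 3 or higher. Where it applies, a patient at the starting level of 125 mg moves to level -1, which is 100 mg (5.5.1): 100 / 125 = 0.80 of the starting dose. The row does not require that GSK2110183 be cleared as the cause, that the sponsor-investigator agree or that the patient consent. Sections 5.5.4 and 5.7.1.1 do not refer to each other. The documents do not print the grade cut-offs. Whether an event just over the third criterion (ALT 3 x ULN with bilirubin 2 x ULN) enters the row therefore depends on where Grade 3 begins: it enters if Grade 3 begins at or below either value, and not otherwise.

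**4. General limits.** Section 5.5.2 recommends withdrawal if toxicity has not settled to Grade 2 or baseline within 14 days. It still allows treatment at a reduced dose once the toxicity reaches Grade 1 or baseline. Sections 5.5.3.1 and 5.5.3.2 link the two drugs' holds at the start of a cycle. None of these is specific to the liver.

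**5. Time on GSK2110183 alone.** Inputs are a 10-day lead-in, 7 combination cycles, 11 maintenance cycles and 28-day cycles (5.1, 5.4.1).

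- Days on GSK2110183 alone: 10 + 11 x 28 = 318
- All days: 10 + 18 x 28 = 514
- Share: 318 / 514 = 0.62

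The synopsis gives 12 maintenance cycles, but 7 + 12 = 19 exceeds its own maximum of 18, so 11 is used. During those 318 days there is no ofatumumab dosing to hold or restart.

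**The case against.** The strongest reply is that the event is already well supervised. The sponsor-investigator reviews every one (5.7.1.1), each is an SAE (6.3.1), causality is judged for each drug (10.4), the investigator may end treatment for harm (5.7), and this is a single-institution trial. This stands as far as it goes. These measures ensure that the event is seen and attributed. They do not say on what conditions GSK2110183 may resume.

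A second reply is that ofatumumab is not consistently protected either. The restart line after the hold asks only for efficacy and an informed patient's wish to continue, with no causality test. This is correct, and it means that the ofatumumab text is not a clean benchmark.

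A third is that 5.7.1.1 may govern ofatumumab alone. Section 5.1.1 presents ofatumumab as the investigational drug, and 5.5.4 is titled for GSK2110183. That reading is possible, but the stop applies to study treatment, a term that 10.2 uses for GSK2110183. Even on that reading, GSK2110183 would have only the catch-all row.

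A fourth is that resuming at a lower dose after a reversible toxicity is ordinary practice. That is fair. The point is not that such a restart is wrong, but that a liver stopping event carries no liver-specific condition for it.

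**Conclusion.** The point holds as a gap in a safety rule: there is no liver-specific restart condition for GSK2110183. It should be corrected, and the primary endpoint and its decision rule are not affected. It rests on reading the stop as covering both drugs, which the text supports but does not state outright.

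A reader might infer more than the documents support:

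- **That GSK2110183 liver events go unreviewed or have no rule at all.** The reviews listed above and the general rules in 5.5.2 to 5.5.4 contradict this.
- **That any liver stopping event leaves the dose open between 0 and 100 mg daily.** That contrast arises only for a patient on 125 mg whose event is drug-related and Grade 3 or higher. An event put down to tumor lysis, for example, is outside the row.
- **That ofatumumab always has to be cleared as the cause before it is resumed.** The line on restart after the hold does not require it.
- **That a number of affected patients can be given.** The documents report no rate from which to estimate one.

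The 62% share assumes that a patient completes all cycles without interruption. It describes the schedule, not risk.

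**What to change.** In 5.7.1.1, change the causality item so that injury due to ofatumumab or GSK2110183 must be excluded. Apply the stop and the rechallenge conditions to each study drug being given at the time: a cause other than liver injury from the drug to be restarted, sponsor-investigator agreement, and patient consent. The line on restart after the hold should point to the same conditions, so that the section no longer contradicts itself.

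In 5.5.4, add a sentence that 5.7.1.1, not the catch-all Grade 3 row, governs GSK2110183 after a liver stopping event.

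Leave the restart dose level, the length of any GSK2110183 hold and re-escalation to the sponsor. The two-week period is justified in the text by the time course of tumor lysis and need not carry over, and the approval for re-escalation in 5.4.1 can stay as it is.

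The cost is wording in two sections, with no new assessments. The downside is that some patients may resume GSK2110183 later or not at all.
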